5.4 Concomitant Medications

5.4.1 The use of any concomitant medication/therapies deemed necessary for patient supportive care and safety are permitted. Other anticancer agents including systemic chemotherapy, radiation therapy, or biologic response modifiers are not permitted during the study. No other investigational drug is allowed during the study. Patients must be off growth factors for five days in order to declare a neutrophil response. Antiemetics may be used for the prevention or treatment of nausea and vomiting.

5.4.2 The administration of drugs known to prolong QTc interval or strong CYP3A4 inhibitors should be administered with caution. Any drug known to inhibit or induce CYP3A4 will likely interact with quizartinib.

The list of drugs that can be associated with Torsades de Pointes or prolonged QT interval can be found online at:

<http://www.azcert.org/medical-pros/drug-lists/bycategory.cfm>.

The list of drugs that interact with CYP3A4 can be found online at:

<http://medicine.iupui.edu/clinpharm/DDIs/ClinicalTable.aspx>

5.4.3 Administration of other antineoplastic agents is prohibited for patients while on this study with the following exceptions: 1) Hydroxyurea may be

used for the first 28 days of therapy. The additional days of Hydrea after 28 days is permitted as clinically indicated, on case by case basis and after discussion with the PI . 2) Administration of intrathecal chemotherapy is allowed when clinically indicated.

6.0 DOSING DELAYS/DOSE MODIFICATIONS

6.1 Toxicity Directly Attributable to Study Drug

Patients experiencing unacceptable toxicity directly attributable to the study drugs should temporarily stop treatment according to the guidelines in the dose adjustment schema.

6.2 Toxicity Grading

Toxicity grading will be according to the NCI CTCAE, v4. To prevent unnecessary morbidity, the following guidelines for dose adjustment for drug-related toxicities are recommended.

6.3 Dose Reductions

Table 2(a): Dose reduction and escalation for Cytarabine + AC220 treatment arm

Dose Level	Cytarabine (mg BID x 10 days)	AC220 (mg/d, uninterrupted)
-3	10	30
-2	15	30
-1	20	30
1 (Starting and target dose)	20	60
2	20	90

Table 2(b): Dose reduction and escalation for AZA+ AC220 treatment arm

Dose Level	AZA (mg/m ² /d x 7 days)	AC220 (mg/d, uninterrupted)
-3	25	30
-2	50	30
-1	75	30
1 (Starting and target dose)	75	60
2	75	90

Dose reductions for non-hematologic toxicity possibly related to study drugs should be performed according to the following table:

Toxicity	Grade	Actions
Non-hematological (excludes myalgia/ arthralgia responding to treatment, inadequately treated nausea, vomiting and diarrhea, or electrolyte abnormalities unless not responding to optimal supplementation)	3	Hold therapy until recovery to Grade \leq 1, then re-start and reduce to the next lower dose level. If toxicity recurs again, hold therapy until recovery to grade \leq 1, then re-start and reduce one additional dose level. Dose reductions below dose level -3 will be considered on an individual basis after discussion with the principal investigator.
Non-hematological, study-drug related	4	Remove from study. An exception can be made if grade 4 toxicity reverses to Grade \leq 1 on or before 14 days of interrupting study drug and re-dosing with AC220 is considered safe and in the best interest of the patient. In those instances treatment may be resumed with a 1 dose-level reduction after discussion with PI and Sponsor.
Non-hematological (excludes myalgia/ arthralgia responding to treatment, inadequately treated vomiting and diarrhea, or electrolyte abnormalities unless not responding to optimal supplementation)	Persistent 2 considered clinically significant or upon patient's request	Hold therapy until recovery to Grade \leq 1, then re-start and reduce to the next lower dose level. If toxicity recurs again, hold therapy until recovery to grade \leq 1, then re-start and reduce one additional dose level. Dose reductions below dose level -3 will be considered on an individual basis after discussion with the principal investigator.
Cardiac Toxicity	QTc > 450 and \leq 480 msec	Check magnesium and potassium levels and correct any abnormalities. If possible, stop any medications that may prolong the QTc interval. Continue quizartinib at the same dose.

Cardiac Toxicity	QTc > 480 and ≤ 500 msec	Check magnesium and potassium levels and correct any abnormalities. If possible, stop any medications that may prolong the QTc interval. Decrease AC220 to next lowest dose level until QTc interval improves to ≤480 msec. AC220 dose may then be escalated to the previous dose if other external factors have been corrected and QTc has remained below 480 msec in at least 3 consecutive ECG separated for at least 2 weeks.
Cardiac Toxicity	QTc interval >500 msec	Check magnesium and potassium levels and correct any abnormalities. Interrupt AC220 and if possible any medications that may prolong the QTc interval. If QTc interval resolves to within 30 msec of baseline value within 7 days resume AC220 at the next lower dose level. If not resolved within 7 days, discontinue therapy permanently.
Cardiac Toxicity	QTc interval >500 or >60 ms change from baseline, and Torsade de pointes or polymorphic ventricular tachycardia or signs/symptoms of serious arrhythmia (i.e., grade 4)	Discontinue therapy

6.3.1 Patients in whom the toxicity occurs or persists beyond the planned completion of drug administration for the cycle will have the dose reductions implemented in subsequent cycles provided the toxicity has resolved as specified in the table above.

6.3.2 If adverse events are clearly associated with one of the drugs, dose adjustments to only that agent may be performed.

- 6.3.3** Dose modifications different than those described above (e.g., dose reductions by 2 dose levels, decreased number of days of administration of either drug continuation of only quizartinib) may be implemented if judged in the best interest of the patient after discussion with the PI and documentation of the rationale for this action.
- 6.3.4** Dose adjustments for only of the drugs may be considered when the adverse event may be clearly associated with only one drug (e.g., QTc prolongation with quizartinib).
- 6.3.5** Patients in whom therapy is held for > 8 weeks due to toxicity will be removed from the trial.

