5.2.7 Quizartinib Administration

Quizartinib will be administered orally at a starting dose of 60 mg daily for the scheduled 28 days in each cycle.

5.2.7.1 If a dose is missed or vomited, the next dose should not be increased to account for missing a dose. The subject should take the next regular dose at the regularly scheduled time.

5.2.7.2 Treatment may be prolonged beyond the planned 28 days of each cycle if the start of the next cycle of AZA or LDAC is delayed. However, if there are adverse events that mandate treatment interruption or it is considered in the best interest of the patient for safety reasons to interrupt therapy, quizartinib administration can be transiently discontinued and re-started as per guidelines in section 6.0.

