5.3 Duration of Therapy

In the absence of treatment delays due to adverse events, treatment may continue until one of the following criteria applies:

1. Clinically significant progressive disease
2. Grade 4 QTc prolongation.
3. Intercurrent illness that prevents further administration of treatment

4. Patient request
5. General or specific changes in the patient's condition render the patient unacceptable for further treatment in the judgment of the investigator.
6. Unacceptable toxicity that in the opinion of the investigator makes it unsafe to continue therapy. This includes patients with grade 4 non-hematological toxicity unless it reverses to grade ≤ 1 on or before 14 days of interrupting AC220.

5.3.1 It is planned that up to a total of 12 cycles of therapy will be administered for patients deriving benefit from this regimen. Continuation of therapy for patients completing 12 cycles of therapy may be considered on a case by case basis after discussion with the principal investigator.

5.3.2 A minimum of 1 full course (defined as the administration of AZA for 7 days or LDAC for 10 days, and quizartinib for 24 days for cycle one, i.e. days 5-28) will be required for a patient to be considered as having received an adequate trial to evaluate efficacy. All patients receiving at least one dose of any of the two drugs will be considered evaluable for toxicity.

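### Section 6.3 gives no effective AC220 reduction for QTc prolongation in a patient already taking 30 mg

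*Combined protocol and SAP*

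**What the plan says.** Tables 1(a)/(b) (section 5.2.1.1) and 2(a)/(b) (section 6.3) list AC220 under a column headed "AC220 (mg/d, uninterrupted". The entries are 90 mg at level 2, 60 mg at level 1, and 30 mg at levels -1, -2 and -3. Below level -1 only the partner drug falls: cytarabine 20, 15, 10 mg twice daily, or AZA 75, 50, 25 mg/m².

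The cardiac rows of section 6.3 then work by dose level.

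- **QTc 481-500 msec:** correct electrolytes, stop QT-prolonging drugs where possible, and "Decrease AC220 to next lowest dose level until QTc interval improves to ≤480 msec". The row has no interruption.
- **QTc above 500 msec:** the same corrections, plus interruption of AC220. If QTc "resolves to within 30 msec of baseline value within 7 days resume AC220 at the next lower dose level". Otherwise: "If not resolved within 7 days, discontinue therapy permanently".
- **QTc prolongation with torsades or signs of serious arrhythmia (grade 4):** discontinue. Section 5.3 item 2 also ends treatment for grade 4 QTc prolongation.

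Other clauses bear on the same patient. Under 5.2.7.2, "quizartinib administration can be transiently discontinued and re-started as per guidelines in section 6.0". Section 5.3 item 6 ends treatment for "Unacceptable toxicity that in the opinion of the investigator makes it unsafe to continue therapy". Section 6.3.3 allows, after PI discussion, changes such as "decreased number of days of administration of either drug". Section 5.2.1.2 sends doses outside the table to the PI.

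**The concern.** QTc prolongation is the dose-limiting toxicity of AC220, and a confirmed QTc above 500 msec counts as a DLT under 5.2.5. Both QTc rows are meant to lower exposure. The row just below them (451-480 msec) shows how the plan writes it when the dose is to stay the same: it says so. For a patient on 30 mg, the level-based rule has nothing to act on.

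Patients can reach 30 mg in several ways: a first QTc event at 60 mg, a one-level reduction for another toxicity, or assignment of a whole arm to level -1 if level 1 exceeds the MTD (5.2.5.3). At stake is repeated or continued exposure at an unchanged dose after a QTc signal, with no default hold at 481-500 and no reduced restart after a value above 500.

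**Working it through.** **Step 1. Apply a one-level reduction to the tables.** The AC220 column is the same in both arms.

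| Level at event | AC220 before | Next lower level | AC220 after | Change |
|---|---|---|---|---|
| 2 | 90 mg | 1 | 60 mg | -30 mg |
| 1 | 60 mg | -1 | 30 mg | -30 mg |
| -1 | 30 mg | -2 | 30 mg | 0 mg |
| -2 | 30 mg | -3 | 30 mg | 0 mg |
| -3 | 30 mg | none | undefined | undefined |

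**Step 2. Put this into the QTc rows.**

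- *481-500 msec:* from -1 or -2 the instructed decrease leaves AC220 at 30 mg; from -3 it cannot be carried out. With no hold in the row, nothing in it lowers exposure.
- *Above 500 msec:* the interruption and the 7-day limit work at any level. Only the restart fails: 30 mg again from -1 or -2, no dose stated from -3.

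**Step 3. Look for a default elsewhere.** The hold in 5.2.7.2 is permissive and refers the restart back to section 6.0. Section 5.3 items 5 and 6 rest on investigator judgment. Sections 5.2.1.2 and 6.3.3 need PI discussion and name no dose. The repeat ECGs in 9.2.5.2 follow a re-escalation after a QTc-related reduction; a restart at an unchanged 30 mg is not one.

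**Step 4. Does resolution off drug show that 30 mg is tolerated?** Section 7.1.2 gives half-lives of about 1.5 days (AC220) and 2 days (AC886). Assuming first-order decline, the fraction left after t days is 0.5^(t / half-life).

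- Day 2: AC220 0.5^(2/1.5) = 0.40; AC886 0.5^(2/2) = 0.50.
- Day 7: AC220 0.5^(7/1.5) = 0.04; AC886 0.5^(7/2) = 0.09.

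The row allows resumption as soon as QTc resolves, so the drug left at restart depends on the day. At either time point exposure is well below steady state, so the recovery was not observed at full 30 mg exposure. After a 7-day interruption, a further 7 days at 30 mg brings AC220 back to at least 1 - 0.04 = 96% of its earlier steady state.

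**Step 5. Size.** Section 2.4 reports QTc above 500 msec in 5% of 38 patients on single-agent 30 mg: 0.05 × 38 = 1.9, about 2 patients. The exact 95% interval for 2/38 is about 0.6% to 18%. If an arm moved to level -1 and treated the 26 further patients in 5.2.5.3, and if the 5% carried over to the combination (assumption), the expected number is 26 × 0.05 = 1.3, and the chance of at least one is 1 - 0.95^26 = 74%. Over the interval, the expected number runs from 26 × 0.006 = 0.2 to 26 × 0.18 = 4.7. The documents do not give the rate of QTc 481-500 msec at 30 mg.

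**The case against.** The strongest reply is that the protocol routes this patient to clinical judgment. Section 5.2.1.2 covers off-table doses, 6.3.3 covers other modifications, 5.3 allows a stop, 6.1 calls for a temporary stop for unacceptable drug-related toxicity, and 6.2 presents the whole scheme as recommended guidelines. The general non-hematologic rows hold therapy until recovery. The worst cases are already covered by a mandatory stop.

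The evidence at 30 mg is also thin. The QTcF reversal described in 2.1 concerns Grade 3 cases, with incidences given at 200 and 300 mg, and the resolution with lower doses in 2.4 refers to prolongations at 90 mg or above. Those events were asymptomatic, and the intermittent 12-60 mg groups in 2.1 showed no time-averaged QTcF effect.

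Much of this stands as a limit on the size of the problem. It does not supply the missing step. The clauses are discretionary or point back to section 6. The general rows restart at the next lower level, which is the same 30 mg, and the specific cardiac rows would normally govern.

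A reader might infer more than the documents support:

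- *That AC220 continues through QTc above 500 msec.* It does not: the row interrupts it, and stops it if unresolved.
- *That the plan directs continuation at 30 mg for 481-500 msec.* The row says to decrease; the unchanged dose results from the table.
- *That restart from level -3 is at 30 mg.* It is undefined.
- *That up to half of patients on 30 mg would exceed 480 msec.* Section 2.4 gives a maximum QTcF change above 30 msec in 47% + 3% = 50%. That puts half above 480 only if every patient starts at the 450 msec limit, and the baseline distribution is not given.
- *That QTc events would lower AZA or cytarabine instead.* Both rows name AC220 alone, and 6.3.4 allows one-drug adjustment when the event is "associated with only one drug (e.g., QTc prolongation with quizartinib".

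**Conclusion.** The concern holds. For a patient already on 30 mg, the 481-500 row has no effective action on AC220. The above-500 row protects the patient during the event but has no reduced restart dose. This follows from the tables and needs no assumption. It is more than missing detail, because a written safety rule for the drug's dose-limiting toxicity does not work when followed.

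The number of patients affected is uncertain and probably small. The only direct figure is about 2 of 38 above 500 msec at 30 mg as a single agent; applying it to the combination is an assumption. Whole-arm exposure arises only if level 1 exceeds the MTD. The rule should be corrected; the design does not otherwise depend on it.

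**What to change.** Add one line to each of the two QTc rows in 6.3 for patients taking AC220 30 mg.

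- **QTc 481-500 msec:** interrupt AC220 until QTc is 480 msec or below and correct cofactors. Resume 30 mg with repeat ECGs on the 9.2.5.2 schedule (24 hours and 7 days), and discontinue AC220 on recurrence. The hold-and-resume step is acceptable here because the event is milder and the ECGs test tolerance on drug.
- **QTc above 500 msec:** discontinue AC220 by default. Allow a restart at 30 mg only after a reversible cause has been corrected, as a documented 6.3.3 exception after PI discussion.

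A lower daily dose is not a ready alternative, since section 7.1.1 describes only 30 mg tablets, and the documents contain no data on alternate-day dosing at 30 mg. The cost is two lines of text and a few extra ECGs, with no added patients. The downside is that a few patients will receive less AC220 than under the current wording.

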- 2.4 Recently, the results of a randomized trial comparing two lower doses of quizartinib were reported. In this trial, patients with relapsed or refractory AML with FLT3 mutation were randomized to receive quizartinib 30 mg or 60 mg orally, daily. A total of 76 patients were enrolled (38 to each arm). The overall composite response rate (CRc, which was the primary endpoint) was identical for the two arms (47%). The overall response rate was slightly higher with 60 mg daily (71%) than with 30 mg daily (61%) because of a higher rate of partial responses in the 60mg arm (24%) compared to the 30 mg arm (13%). QTc prolongation to >500 msec (the dose limit⁹⁸ toxicity for quizartinib) occurred in only 3% with 60 mg and 5% with 30 mg. When comparing these results with a prior study exploring higher doses (90 mg, 135 mg, and 200 mg) it is clear that the rate of CRc is identical at all dose levels with some increase in PR with progressively higher doses. However, QTc prolongation is clearly dose dependent and prolongations >60 msec from baseline occur in 40% or more of the patients treated at doses of 90mg or above, exceeding the threshold of acceptable grade 3 toxicity for the standard definition of MTD. Although these prolongations have been asymptomatic and transient, resolving with lower doses, based on this new data we have decided not to explore a dose level of 90 mg daily and expand 60

mg (i.e., the starting dose level) for the phase 2 portion of the study provided MTD is not exceeded as defined in the protocol section 5.2.5. If MTD is exceeded at this dose level, 30 mg will be explored.

	2689-CL-2004		AC220-002 (Cohort 2)		
	30 mg/day (N = 38)	60 mg/day (N = 38)	90 mg/day (N=57)	135 mg/day (N=67)	200 mg/day (N=12)
Best Response					
CRc Rate	47%	47%	47%	45%	42%
PR Rate	13%	24%	25%	28%	50%
Maximum change in QTcF from baseline (msec)					
≤ 30	50%	44%	9%	9%	0%
> 30 to ≤ 60	47%	36%	46%	51%	8%
> 60	3%	19%	46%	39%	92%

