6.5 Inpatient Dose Escalation for Patients Treated at Dose Level -1 or Lower

Inpatient dose escalation will be permitted for these patients provided:

- 6.5.1** Patient has completed ≥ 1 cycle at dose level -1 or lower, and
- 6.5.2** Patient has not experienced any grade 3 or higher non-hematologic toxicity, and
- 6.5.3** Patient has not experienced hematologic DLT, and
- 6.5.4** At least 3 patients have been treated at the next higher dose level and followed for at least 28 days without experiencing DLT.
- 6.5.5** Patients who have experienced no QTc prolongation above 480 msec in whom optimal anti-leukemia effect has not been reached may have the dose of quizartinib increased to by one dose level. Patients who have such dose escalation will have an EKG done 24 hours and 7 days after dose escalation. No dose escalation above 90 mg/day will be allowed.
- 6.5.6** Because of the increased risk of QTc prolongation in women treated at doses > 90 mg/day in prior studies with AC220, dose escalation above 90 mg/day is not allowed in women.

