7.0 AGENT FORMULATION AND PROCUREMENT

7.1 Quizartinib (AC220)

7.1.1 Description

The chemical name of the investigational product, quizartinib, is N-(5-tert-Butyl-isoxazol-3-yl)-N'-[4-[7-(2-morpholin-4-yl-ethoxy)imidazo[2,1-b][1,3]benzothiazol-2-yl]phenyl] urea dihydrochloride salt.

AC220 is supplied as tablets each containing 30 mg AC220 (26.5 mg free base) and 300 mg HP β CD. The tablets also contain microcrystalline cellulose, magnesium stearate, and Opadry® II 85F18422 white film coating. They are packaged in high density polyethylene bottles, each containing 30 tablets, with child-resistant caps.

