9.2 Evaluation During Treatment

- 9.2.1 Physical exam at the start of each cycle (± 5 days) for the first 2 cycles, then every 2-3 cycles and documentation of all concomitant medications.
 - 9.2.1.1 Patients will keep a diary for drug administration of self-administered drugs (cytarabine and AC220)
- 9.2.2 CBC, platelet count, differential once weekly for the first 3 cycles, then every 2-4 weeks (all ± 2 days) (differential can be omitted if WBC is $\leq 0.5 \times 10^9/L$)
- 9.2.3 Creatinine, total bilirubin, ALT, K, Mg, Ca, sodium, chloride, and CO₂ on day 5 prior to start of AC220, then weekly for the first 3 cycles, then every 2-4 weeks (all ± 2 days) .
- 9.2.4 Bone marrow aspiration on day 28 (± 7 days) of cycle 1, then every 1-3

cycles.

9.2.5 EKG will be performed on day 1, day 5, day 8, and day 12 of the first cycle (all ± 2 days) Day 1 and day 8 ECG are collected pre-dose; day 5 are collected pre-dose and 4 hrs (± 2 hrs) post-dose; day 12 are collected 4 hrs (± 2 hrs) post-dose. Then ECG to be done on day 1 of each cycle for cycles 2 and 3 before initiation of quizartinib and 4 hr (± 2 hrs) post dose, then pre-dose every 2-3 cycles. EKG may be omitted if patient has not received study drug (AC220) in the 48 hrs preceding the time when EKG is done. EKG for the first 3 cycles will be done in triplicate. Day 5 pre AC-220 will be used as baseline.

9.2.5.1 On patients in whom quizartinib is escalated to 90 mg daily as described in section 6.5.5 or who start therapy with a drug that may prolong QT/QTc or that is a strong CYP3A4 inhibitor or inducer, an EKG will be required 24 hrs (± 6 hrs), 7 days (± 2 days) and 14 days (± 2 days) after the dose increase or after the start of such drug.

9.2.5.2 Patients who had their dose reduced because of QTc prolongation and have their dose re-escalated as described in section 6.3 will have an EKG repeated 24 hrs (± 6 hrs) and 7 days (± 2 days) after re-escalation.

9.2.5.3 The QTc interval will be calculated by Fridericia's correction factor (QTcF). The 12-lead EKG evaluation will consist of 3 separate EKGs obtained at least 5 minutes apart.

9.2.6 Correlative studies on days 1, 8 and 15 of each cycle up to the first 4 cycles (all ± 2 days). (Optional – See Section 8.0).

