^k EKG will be performed on day 1, day 5, day 8, and day 12 of the first cycle (all ± 2 days) Day 1 and day 8 ECG are collected pre-dose; day 5 are collected pre-dose and 4 hrs (+/- 2 hrs) post-dose; day 12 are collected 4 hrs (+/- 2 hrs) post-dose. Then ECG to be done on day 1 of each cycle for cycles 2 and 3 before initiation of quizartinib and 4 hr (+/-2 hrs) post dose, then pre-dose every 2-3 cycles. EKG may be omitted if patient has not received study drug (AC220) in the 48 hrs preceeding the time when EKG is done. EKG for the first 3 cycles will be done in triplicate. Day 5 pre AC-220 will be used as baseline.

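### No ECG is required after AC220 is restarted following a QTc above 500 msec, so the next one can be weeks away

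*Combined protocol and SAP*

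**What the plan says.** The QTc >500 msec row of the table in section 6.3 calls for electrolyte correction, interruption of AC220 and, where possible, interruption of other QT-prolonging drugs. It continues: "If QTc interval resolves to within 30 msec of baseline value within 7 days resume AC220 at the next lower dose level". The alternative is "If not resolved within 7 days, discontinue therapy permanently".

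ECGs outside the routine schedule are required in these situations:

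- Section 5.2.5: a reading above 500 msec is repeated in triplicate within 2 hours.
- Section 6.5.5: "Patients who have such dose escalation will have an EKG done 24 hours and 7 days after dose escalation". This applies to patients who have never exceeded 480 msec.
- Section 9.2.5.1: escalation to 90 mg, or the start of a QT-prolonging drug or a strong CYP3A4 inhibitor or inducer.
- Section 9.2.5.2: "Patients who had their dose reduced because of QTc prolongation and have their dose re-escalated as described in section 6.3 will have an EKG" at 24 hours and at 7 days.

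Routine ECGs (section 9.2.5 and Appendix AA, footnote k) fall on days 1, 5, 8 and 12 of cycle 1, on day 1 of cycles 2 and 3, and every 2 to 3 cycles after that. A further rule reads "EKG may be omitted if patient has not received study drug (AC220) in the 48 hrs" before the scheduled time.

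On dose, Table 2(b) in 6.3 ("Dose reduction and escalation for AZA+ AC220 treatment arm") and its cytarabine counterpart, Table 2(a), give 30 mg of AC220 at levels -1, -2 and -3 alike. Section 7.1.1 says "AC220 is supplied as tablets each containing 30 mg AC220 (26.5 mg free base").

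**The concern.** QTc prolongation is the dose-limiting toxicity of AC220. The plan allows re-exposure after that toxicity but sets no ECG to see whether it recurs. The monitoring also runs the wrong way round: a patient who reached 481 to 500 msec and is later re-escalated gets ECGs at 24 hours and 7 days, while a patient who exceeded 500 msec and restarts gets neither.

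The lower dose does not remove the risk. Section 2.4 reports that QTc >500 msec "occurred in only 3% with 60 mg and 5% with 30 mg". Because three consecutive levels share the same AC220 dose, a patient whose event occurs on 30 mg can move down a level and restart on 30 mg. Contributing QT-prolonging drugs are stopped only where possible, and one that is continued through the restart is not newly started, so it does not trigger 9.2.5.1.

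This is a patient-safety point. It does not bear on the response endpoint or on the DLT stopping boundaries.

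**Working it through.** The plan states no interval from restart to next ECG, so there is no figure to reproduce. The check is a reading of the triggers followed by calendar arithmetic.

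**Step 1: does any trigger reach a restart?**

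| Provision | Why it does not apply |
|---|---|
| 5.2.5 | Confirms the event itself; it precedes any restart |
| 6.5.5 | Limited to patients never above 480 msec |
| 9.2.5.1 | Needs escalation to 90 mg or a newly started drug |
| 9.2.5.2 | Needs a re-escalated dose; in 6.3 re-escalation appears only in the >480 to ≤500 msec row |
| 5.2.7.2 | Refers restarts back to section 6.0 |

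Only the routine schedule remains.

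**Step 2: time to the next routine ECG.** The inputs are a restart 0 to 7 days after the event (6.3), 28-day cycles (5.2.6) and the ECG days in 9.2.5. Cycle 2 day 1 is study day 29 and cycle 3 day 1 is day 57. Later ECGs come 2 × 28 = 56 or 3 × 28 = 84 days apart.

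Gap = day of next scheduled ECG − day of restart.

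| Event found at | Restart day | Gap to next ECG |
|---|---|---|
| Cycle 1 day 5 | 5–11 | 1–4 days (day 8 or day 12 ECG) |
| Cycle 1 day 8 | 8–11 | 1–4 days (day 12 ECG) |
| Cycle 1 day 8 | 13–15 | 29 − 15 = 14 to 29 − 13 = 16 days |
| Cycle 1 day 12 | 12–19 | 29 − 19 = 10 to 29 − 12 = 17 days |
| Cycle 2 day 1 | cycle days 1–8 | 29 − 8 = 21 to 29 − 1 = 28 days |
| Cycle 3 day 1 or later, ECG every 2 cycles | 0–7 days on | 56 − 7 = 49 to 56 days |
| Cycle 3 day 1 or later, ECG every 3 cycles | 0–7 days on | 84 − 7 = 77 to 84 days |

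A day 5 or day 8 event restarted on day 12 itself meets that day's 4-hour post-dose ECG. If that tracing is taken before the restart dose, the gap is 29 − 12 = 17 days.

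Sensitivity: 21-day cycles (early starts are allowed by 5.2.6.1) give 22 − 19 = 3 to 22 − 12 = 10 days for the day 12 event and 42 − 7 = 35 to 63 days for late events. A delayed cycle with AC220 continued (5.2.7.2) lengthens every gap that ends at the start of a cycle. The ±2-day window on the day 12 ECG widens 10–17 to 29 − 21 = 8 through 29 − 10 = 19 days.

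**Step 3: exposure by then.** Section 7.1.2 gives half-lives of about 1.5 days (AC220) and 2 days (AC886). Starting from no drug, the share of steady state at time t is 1 − 0.5^(t/half-life).

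| Time after restart | AC220 | AC886 |
|---|---|---|
| 24 hours | 37% | 29% |
| 7 days | 96% | 91% |
| 10 days | 99% | 97% |

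Exposure at the resumed dose is essentially complete before the next required ECG in every case from cycle 1 day 12 onward.

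**Step 4: number of patients.** The phase II maximum is 26 + 50 + 50 + 50 = 176 (section 12.3). Assuming the monotherapy rates in 2.4 carry over, 0.03 × 176 = 5.3 and 0.05 × 176 = 8.8, so about 5 to 9 exceed 500 msec. Assuming 50% to 100% of them recover within 7 days and restart, 0.5 × 5.3 = 2.6 to 8.8, or about 3 to 9 patients.

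**The case against.** The strongest objection concerns frequency. Section 2.1 reports that, in the first-in-human study, QTcF above 500 ms appeared between 2 hours after the first dose and day 8 of dosing. AC220 starts on study day 5 here, so day 8 of dosing is day 12, and those events would fall where ECGs are densest. The 49 to 84 day gap needs a first event at cycle 3 day 1 or later, and section 2.1 describes none. This stands: 49 to 84 days is a worst case and not what a typical patient would face. It leaves the 10 to 17 days after a day 12 event untouched, and that event lies inside the reported onset window.

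Second, the restart has safeguards. QTc must be back within 30 msec of baseline, electrolytes are corrected, and potassium and magnesium are checked weekly through cycle 3. After a quick restart from 60 mg, residual drug means the pre-restart ECG already tests part of the new exposure: assuming linear kinetics, one half-life (1.5 days) leaves about the 30 mg level. That helps early restarts only; at 7 days the residue is 0.5^(7/1.5), about 4%.

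Third, 6.3.4 lets AC220 alone be adjusted for QTc prolongation, and 5.2.1.2 and 6.3.3 allow off-table changes after discussion with the principal investigator. A restart at an unchanged 30 mg is therefore possible but not compelled.

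Fourth, the counts are soft. With 38 patients per arm, 3% and 5% are about 1 and 2 patients, the higher rate is at the lower dose, and 176 is a ceiling.

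Finally, nothing forbids a clinically indicated ECG. But the plan spells out ECGs for lesser triggers, and section 9.2 allows care to be shared with local physicians, who are sent the written evaluation schedule.

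**Conclusion.** The concern holds. As written, a patient restarted on AC220 after a QTc above 500 msec has no required ECG until the routine schedule supplies one: nominally 10 to 17 days after a cycle 1 day 12 event, 21 to 28 days after cycle 2 day 1, and 49 to 84 days in the worst case. Restarts within a few days of a cycle 1 day 5 or day 8 event are covered, so the gap is not universal.

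The intervals rest on 28-day cycles, events found at scheduled ECGs and nominal visit days. The estimate of 5 to 9 patients, with about 3 to 9 restarting, rests on the two assumptions in step 4. The number affected is small, but the event is the drug's dose-limiting toxicity and the correction is cheap, so the change should be made.

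**What to change.** Extend 9.2.5.2 so that any resumption of AC220 after an interruption for QTc >500 msec triggers ECGs at the times that section already uses: 24 hours (± 6 hours) and 7 days (± 2 days) after the restart. Add a cross-reference in the >500 msec row of 6.3. The 7-day ECG matters most, because exposure at the resumed dose is then above 90% of steady state for both AC220 and AC886.

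The cost is one phrase and one cross-reference, plus two ECG time points for each patient who restarts (2 × 3 = 6 tracings if done in triplicate as in 9.2.5.3). At most about 9 patients would be involved under the assumptions above.
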